**Table 1. Participant Characteristics by Site – mean (SD)**

	Jamaica	Maywood	Nigeria	Seychelles	S. Africa
n (M/F)	41 (18/23)	36 (16/20)	38 (20/18)	45 (22/23)	38 (16/22)
Age (yrs)	37.9 (8.6)	38.3 ± 10.1	38.9 ± 13.2	35.2 ± 5.7	27.2 ± 5.0
BMI					
males	23.6 (3.5)	27.3 ± 6.5	22.5 ± 2.9	26.6 ± 3.3	21.8 ± 2.0
females	30.6 (5.3)	33.7 ± 9.4	26.2 ± 6.4	26.9 ± 6.4	29.8 ± 7.3
Activity Counts					
males (cts/d)	364040 (158584)	313988 ± 217868	241191 ± 103401	275078 ± 130813	379480 ± 159859
females	209277 (94637)	280929 ± 175078	181312 ± 105667	170670 ± 76242	293548 ± 182584
AEE (kcal/d)					
males	1050 (306)	1090 ± 387	688 ± 253	902 ± 254	911 ± 329
females	884 (306)	1090 ± 566	608 ± 230	617 ± 292	1000 ± 514
AEE/kg (kcal/kg/d)					
males	15.06 (3.76)	13.25 ± 5.71	10.45 ± 3.83	11.45 ± 3.08	14.37 ± 5.35
females	11.13 (3.75)	12.42 ± 5.66	9.14 ± 3.88	8.73 ± 3.16	13.29 ± 6.06
AEE adj. for wt					
males (kcal/d)	1094 (271)	985 ± 426	761 ± 262	866 ± 239	1011 ± 319
females	838 (287)	970 ± 532	660 ± 220	667 ± 227	999 ± 467
Pop. Mean BMI*					
males	23.7 (4.5)	26.7 (5.5)	22.6 (4.5)	25.1 (4.4)	22.9 (6.0)
females	28.0 (6.4)	29.8 (8.1)	22.9 (6.0)	27.6 (6.3)	27.1 (9.1)

\* Population mean BMI for 25-45 year olds based on representative sampling

The absolute activity EE levels are supported by data on the % of time spent in sedentary vs. moderate activity, with Jamaican and South African males, who were primarily laborers, spending less time in sedentary activity than Nigerian or Seychelles women, as recorded by the accelerometer (Table 2). There was an inverse association between activity counts and BMI (Figure 4) indicating a cross-sectional relationship between adiposity and PA. We acknowledge that heterogeneity exists by gender, but caution against interpretation of sub-groups given the small sample size.

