Although the study is not powered to test for differences in the association across sites (i.e., effect modification), we will undertake this task to ensure that large differences among the correlation coefficients do not exist. In addition, sites in which the correlation coefficient is deemed to be similar will be combined, and then comparisons of the correlations will be performed. For the sake of illustration, assume that 2 sites ( $n = 150$  individuals) are compared to other 2 sites ( $n = 150$  individuals). Thus, a two-sample, one-sided test of the correlations, assuming -0.4 versus -0.65, will yield over 91% power, whereas the power will be over 80% for comparison of -0.45 and -0.65, and between -0.35 and -0.6 the power is greater than 85%. Combining the data samples from all 5 sites and assuming constant

association will demonstrate a correlation between AEE and change in body composition of -0.15 or smaller (larger in absolute value) with over 83% power.

3) Mean levels of AEE are negatively related to mean levels of obesity/relative weight among the populations.

As previously demonstrated, sample sizes within sites will allow us to rule out correlations larger than 0.33 (absolute value), even when AEE is determined by DLW. Furthermore, we have estimated (cf. Preliminary Studies) that the within-site correlation between AEE and body composition of individual data could be as large as 0.6. We anticipate that the correlation between mean AEE levels and mean body composition will exceed 0.85. This estimate is justified in the following manner. A Fisher's Z-transformation 5%-significance test will have over 55% power to detect this correlation with 5 values corresponding to the 5 sites of the study. However, after dividing our samples by gender there will be 10 observations (2 X 5 countries), resulting in over 95% statistical power. Assuming an effective sample size of 7, to account for within-country correlations, the statistical power is 80%. Note that additional power will be gained when weighted linear regression methods are applied to estimate the correlation (slope) between AEE and body composition using meta-regression. Given the strong a prior hypothesis we can also compare mean AEE in the groups with the highest and lowest rates of obesity to test the ecological association.

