In this instance, we acknowledge that we are forced to make the assumption that important relationships will be inherently strong statistically. This assumption is justified since the unit of the analysis will be the average for the entire group in each site, and therefore estimated with precision. For example, in our study of 11,000 individuals in 8 populations we demonstrated a correlation of 0.85 between mean BMI and prevalence of hypertension [123]. To enhance our ability to find these relationships, we have selected populations from across the full range of BMI (e.g., from 21-30). We are also fully aware of the possibility of "ecological confounding" in these analyses. Thus, while a strong correlation could be observed, the causal process could be entirely different from, but simply co-linear with, the AEE relationship. We will guard against this outcome by testing the individual-level relationships first, as discussed previously.

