## D.8 Limitations

This study is based on the premise that objective measurement of EE will be required to fully understand the causes of the on-going secular trends in obesity. Given prior research on the role of specific sedentary activities, it is reasonable to test the hypothesis that AEE will vary across the social settings we have chosen to study. The value of our study will be in quantifying the overall magnitude of this difference and its within-site relationship. We recognize that it is possible that increases in energy intake—rather than expenditure—could be the determining, or even sole factor, in weight gain and diabetes risk; demonstrating the absence of a PA-obesity relationship will directly support this alternative hypothesis. We will capture data on EI from questionnaires as well, although we recognize its limitations.

On the other hand, the net positive energy balance required to cause gradual weight gain can be quite subtle (in the range of 20-40 kcal/d for adults). Given that this net excess is likely to be due to a combination of both decreased AEE and increased caloric intake, the contrast in population means for AEE could be hard to define. As in all such etiologic studies, therefore, we run the risk of a false negative due to low power. This result, however, would not be uninformative since it would be important to know that large mean shifts in AEE were not driving this epidemic. At the same time, a wide distribution of AEE levels can be anticipated among participants within each site, and we anticipate finding important relationships in the individual-level analyses. The entire success of the project, therefore, does not rest on the group comparisons.

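### The Hypothesis 3 power rests on an assumed correlation of about 0.85 for which the plan gives no evidence involving AEE, yet a null result is to be read as informative

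*Combined protocol and SAP*

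**What the plan says.** Hypothesis 3 is one of the four primary hypotheses listed in D.7.1. For its power, D.7.2 item 3 states: "We anticipate that the correlation between mean AEE levels and mean body composition will exceed 0.85. This estimate is justified in the following manner". Three power figures come after it:

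- Five site means: "A Fisher's Z-transformation 5%-significance test will have over 55% power to detect this correlation with 5 values corresponding to the 5 sites".
- Ten sex-by-site means: "there will be 10 observations (2 X 5 countries), resulting in over 95% statistical power".
- An effective sample size of 7, allowing for correlation within country: 80%.

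Item 3 does not say whether the test is one- or two-sided. D.7.2 then concedes that a strong relationship has to be assumed. It argues that group means are precise and that the sites span a wide BMI range, and gives one numerical precedent: "we demonstrated a correlation of 0.85 between mean BMI and prevalence of hypertension". B.7 also reports 0.85, for BMI and sodium with blood pressure across populations.

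D.8 admits that the group comparison may give a false negative through low power. It nevertheless calls such a result informative, because "it would be important to know that large mean shifts in AEE were not driving this epidemic". B.9 similarly says that absence of an association would mean declining AEE is unlikely to be driving the rise in obesity.

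**The concern.** A power figure is only as good as its effect size. Here the sentence that promises a justification leads into the power calculation, which takes 0.85 as given. The precedents show that some group-level correlations reach 0.85. They do not show that mean AEE and mean adiposity do. Precise group means make an estimate stable; they do not make the underlying relationship strong.

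What is at stake is the reading of a null. If the true correlation is appreciably weaker than 0.85, a non-significant result is a common outcome even though a real relationship exists. A reader who relies on the printed 80% together with D.8 and B.9 would take that null as evidence against AEE as a population driver of obesity.

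**Working it through.** **Inputs.** |r| = 0.85, 5% Fisher's Z test, n = 5, 7 and 10 (D.7.2 item 3); group means from Table 1; the Nigeria-US contrast from Table 3.

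**1. Reproduce the plan.** Power = Φ(atanh|r| × √(n − 3) − z), with z = 1.645 (one-sided) or 1.960 (two-sided), and atanh(0.85) = 1.256.

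- n = 5: 1.256 × √2 − 1.645 = 0.13, giving 55.2%.
- n = 7: 1.256 × 2 − 1.645 = 0.87, giving 80.7%.
- n = 10: 1.256 × √7 − 1.645 = 1.68, giving 95.3%.

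All three printed figures match one-sided. Two-sided they would be 42.7%, 71.0% and 91.4%, which do not match.

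**2. Vary the correlation at n = 7.**

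| \|r\| | One-sided | Two-sided |
|---|---|---|
| 0.85 | 81% | 71% |
| 0.70 | 54% | 41% |
| 0.60 | 40% | 28% |

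The value 0.60 is the plan's own upper figure for the within-site correlation. For 80% one-sided power, |r| must be tanh((1.645 + 0.842)/2) = 0.846, so the plan's formula leaves no slack. The normal approximation is somewhat pessimistic at n = 7: simulating the same one-sided test under bivariate normality gives about 87%, 60% and 44%. The steep fall remains.

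**3. Look at the plan's own means.** Table 1 gives AEE and pilot BMI for the ten sex-by-site groups, and a further BMI row described as "Population mean BMI for 25-45 year olds based on representative sampling". Pearson correlations, pilot BMI / population BMI:

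| Activity measure | Ten groups | Five sites, sexes averaged equally |
|---|---|---|
| AEE, kcal/d | +0.35 / +0.39 | +0.81 / +0.78 |
| AEE per kg | -0.13 / -0.06 | +0.42 / +0.42 |
| AEE adjusted for weight | +0.03 / +0.10 | +0.55 / +0.55 |
| Activity counts | -0.31 / -0.22 | +0.39 / +0.40 |

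None is near -0.85.

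**4. Ask how firm that is.** Groups hold 16 to 23 people. At n = 7 the 95% interval around -0.31 is tanh(atanh(-0.31) ± 1.96/2), or -0.86 to +0.58, which still contains -0.85. Table 3, by doubly labeled water in 150 Nigerian and 180 US women, gives AEE per kg of 13.5 and 10.0, with body fat of 29.3% and 39.8%. That is the hypothesised direction. Table 1 has the reverse for women from these two countries: 9.14 and 12.42. Putting the Table 3 AEE values into those two cells moves the ten-group correlation of AEE per kg with population BMI from -0.06 to -0.53. This mixes two measurement methods, so it is illustrative only, but it shows how much two cells can matter.

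**5. Ask what a null could show at n = 7.** One-sided significance needs an observed r below -tanh(1.645/2) = -0.68. An observed r of -0.5 is therefore non-significant, yet its 95% interval is tanh(-0.549 ± 0.98), or -0.91 to +0.41. The interval excludes -0.85 only when the observed r is above -tanh(1.256 − 0.98) = -0.27. Results between -0.68 and -0.27 are neither significant nor able to rule out the design value.

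**The case against.** The best defence is that the plan is open about this. D.7.2 says a strong relationship is a forced assumption, D.8 concedes a possible false negative, and D.8 adds that the project does not depend on the group comparisons. That stands, and it makes the fault milder. It does not supply evidence for 0.85, nor does it reconcile conceding low power with reading the null as informative.

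A second defence is that D.8 speaks of contrasts in mean AEE, which are estimated far more precisely than a correlation over a handful of points. With 500 per site and SDs of roughly 250 to 570 kcal/d (Table 1), the 95% half-width of a two-site difference is 1.96 × SD × √(2/500), about 31 to 71 kcal/d. This partly stands: a flat AEE profile across sites could itself count against large shifts. But D.8 states no such criterion, and Hypothesis 3 is tested as an association.

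A reader might also infer from Table 1 that the plan's data refute -0.85, or that -0.31 is the best value they support. Neither follows. The groups are small and C.2.1 itself cautions against interpreting sub-groups. The South African sample is younger (mean 27.2 years, against 35 to 39 elsewhere). Item 3 concerns body composition whereas Table 1 has BMI. AEE in kcal/d tends to rise with body weight. Table 3 points the other way. Nor is a null the likely result under every moderate relationship, since power at 0.70 is still 54%. Finally, D.7.2 expects some gain from weighted meta-regression; it does not quantify it, and no allowance is made for it here.

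**Conclusion.** The concern holds in a limited form. The printed power is computed correctly, but it is conditional on |r| of about 0.85 and on an unstated one-sided 5% test. The plan calls that value justified while offering only the calculation itself and precedents that do not involve AEE. Its pilot means do not support -0.85 (-0.31 to +0.39 over ten groups, all positive over five sites), and they do not disprove it. At effective n = 7, power falls from 81% to 54% at 0.70 and 40% at 0.60. A non-significant ecological result therefore cannot by itself carry the meaning that D.8 and B.9 give it.

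These sizes rest on the plan's own Fisher approximation and on its effective sample size of 7, which is asserted without derivation.

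**What to change.** In D.7.2 item 3:

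- Delete the sentence claiming that the estimate is justified. Say instead that 0.85 is an assumption borrowed by analogy from other variables.
- State that the test is one-sided.
- Print power at effective n = 7 for 0.85, 0.70 and 0.60: 81%, 54% and 40% one-sided (71%, 41% and 28% two-sided). Do not print -0.31 as the best value the plan's data support.

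In D.8 and B.9, state that a non-significant ecological result will be reported as the correlation or slope with its 95% confidence interval. A strong AEE relationship will be ruled out only if that interval excludes a pre-stated value, such as the design value of -0.85 for the correlation. Otherwise the result is called inconclusive.

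The cost is wording and a three-row table, with no extra participants or data. The stated power becomes less favourable, and a null ecological result will often have to be called inconclusive.

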Descriptive epidemiology is usually the only available tool that can be used to examine etiologic processes in chronic disease. For many “common source” diseases, however, methodological problems undermine its effectiveness. Within a homogeneous society some degree of exposure may be universal, and the relevant quantitative variation can be hard to characterize. This is often complicated by large *within-person* relative to *between-person* variation in the exposures which makes person-level analyses imprecise. The large contrasts obtained by comparing social groups as the unit of analysis and the marked shifts that occur among migrants can help focus attention on the key exposures. For example, in ICSHIB low correlations were noted between BMI and Na with BP at the individual level (.01-.15); however, these rose to 0.85 when populations were the unit of analysis. As with all study designs, however, there are trade-offs in cross-cultural studies. For example, a concern sometimes raised is the “ecologic fallacy,” whereby group-level relationships are falsely inferred to be causal at the individual level [82]. We are well aware of this potential threat and address it further in the analytic section of the Methods. With consistency at both levels and control for confounding, however, these relationships can be inferred with confidence. Likewise, once a strong hypothesis has been established, larger within-population studies can be justified.

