Following transformation of the appropriate exposure and outcome variables, Fisher's Z-transformation test will be applied in order to test hypotheses involving correlations. The resulting parametric test will be more powerful than other distribution-free approaches. The results will be corroborated by applying Spearman rank correlations and another parametric test based on the concordance coefficient introduced by Lin [182] and later extended by Chinchilli and colleagues to include repeated measures [183]. Lin's concordance correlation allows the comparison of the correlations accounting for possible differences in the mean values of the two variables under consideration. Furthermore, approximate permutation tests [184, 185] will be implemented using each of the three statistics: Pearson, Spearman and Lin's concordance, to compare agreement of the association between AEE and BMI across the three groups under investigation.

Correlation coefficients will be estimated using the Pearson correlation and confidence intervals constructed after applying the Fisher's Z-transformation. Furthermore, computer intensive statistical methods, such as bootstrapping, will be used to construct confidence intervals for both parametric and nonparametric approaches. Comparisons of these correlations will be carried out using this statistic for 1 and 2 samples [186], as well as approximate permutation tests [184, 185]. In addition, multivariate regression analysis will be fit to adjust for potential confounders. Confounders will include age, gender, and any other significant

predictors defined by the univariate analyses. Potential non-linear functions will be explored to see if they fit the data better. Sub-group analyses will be undertaken, with participants in each site divided by gender.

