#### D.7.1.3 Comparison of Mean AEE Levels Among Sites

The 2 sample t-test will be used to compare means of the primary continuous variables, e.g., BMI, PA, weight, and height. Relevant co-variates will be identified from the within-site analyses and added using multivariable models [186, 190]. We recognize that some modifying factors within sites may not have the same significance across sites, and we will be very careful how variables are chosen for these analyses. Finally, we will test whether the regression slopes of the PA-BMI relationship varies significantly among any pair of sites (i.e., test for interaction).

The association between mean levels of AEE and mean levels of obesity/relative weight will be assessed using regression analysis, following a meta-regression type of approach. That is, mean AEE values will be regressed on mean obesity/relative weight values, weighting by the inverse of the squared standard error of the mean AEE values [191]. This is a widely-used approach in meta-analysis [192]. It is recognized that EI is an important potential confounder of the associations at the individual level. We will estimate the median (and other quantiles of the distribution) usual intake of nutrients (e.g. fat, percent fat) using methods developed by the ISU research group [179, 193] and include them in the meta-regression models.

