## D.7.2 Power Analysis

A statistical justification for the selected sample size is provided for each aim of the study according to the suggested analytical plan. Sample size estimation for each of these hypotheses will be obtained, and the maximum number required to test them with sufficient power (80% or higher) will be selected.

- 1) PA is negatively related to percent body fat and CV risk factors in the study populations at baseline.

It has been previously estimated (cf. Preliminary Studies) that the correlation between PA, measured with DLW, and body composition is between -0.6 and -0.5. A correlation of -0.33 or smaller (larger in absolute value) will be detectable with 83% power and maximum probability of type I error alpha = 5% using a one-sided Fisher's Z test and 75 subjects per site [194].

- 2) PA is negatively related to change in body fat composition.

- a) *Physical Activity Measured by Accelerometer:*

PA, measured by the accelerometer, is associated with changes in body composition. For design purposes we will use the approach described above in the analysis section (see D.7.1.2. method 3). That is, two AEE groups will be formed by using the median AEE as the cut point. A method developed by Frison and Pocock [195] will be applied to compare mean changes between groups in a longitudinal analysis, adjusting for baseline values. In this method the following assumptions are made: the correlation between any 2 weight determinations is ~ 0.60 and the minimum acceptable difference between the means is 0.25 standard deviations (i.e., effect size equals 0.25) [186]. There will be one baseline measure of weight and two follow-up measurements. An analysis of covariance approach will be used to adjust for baseline values. Thus, to detect the pre-specified minimum difference with 90% statistical power we will need to accrue 460 subjects per AEE group (230 in the Low and 230 in the High group). We will accrue a total of 500 individuals per site in anticipation of a conservative total attrition rate of ~ 20%.

- b) *Physical Activity Measured by Doubly Labeled Water:*

The correlation between AEE and change in body composition is anticipated to be weaker (i.e., smaller in absolute value) than that observed between AEE and body composition at baseline. Data from previous studies (cf. Section C: Preliminary Studies) suggest that the association between AEE and body composition remains constant across studies.

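### The 80% power stated for the between-population hypothesis (H3) rests on sex-by-site means, a one-sided test and no covariates, which is not the unit stated next to it or the model in D.7.1.3

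*Combined protocol and SAP*

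**What the plan says.** D.7.2 sets the standard for every hypothesis: "the maximum number required to test them with sufficient power (80% or higher) will be selected". For H3 it assumes a correlation above 0.85 between mean AEE and mean body composition, tested with Fisher's Z at 5%. Five site values give a little over 55% power. The text then says that "after dividing our samples by gender there will be 10 observations (2 X 5 countries), resulting in over 95% statistical power", and adds a discount: "Assuming an effective sample size of 7, to account for within-country correlations, the statistical power is 80" percent. It says that weighted regression will add power, without a figure. Sidedness is not stated for this test.

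The following paragraph defends the assumption of a strong correlation on the ground that "the unit of the analysis will be the average for the entire group in each site". B.7 uses the same unit for its precedent, where low individual-level correlations are reported and "these rose to 0.85 when populations were the unit of analysis".

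D.7.1.3 specifies a weighted meta-regression of mean AEE on mean obesity or relative weight. It does not say whether the means are by site or by sex within site. Estimated quantiles of usual nutrient intake are to be computed, and the plan will "include them in the meta-regression models"; how many is not fixed. Sex is not named there. A general sentence earlier in that section reads "Relevant co-variates will be identified from the within-site analyses and added using multivariable models", and the individual-level baseline analysis states "Confounders will include age, gender".

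**The concern.** H3 is one of the four hypotheses listed as primary in D.7.1. From the plan as written, a reader cannot tell whether it has 55% or 80% power, because the power text and the paragraph justifying it use different units. Neither figure allows for the intake covariates that the plan says it will fit, and with five to ten points each covariate costs a visible share of the information.

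The second issue arises only if the ten sex-by-site means are used. Men and women differ in both BMI and activity. Without a sex term, that difference contributes to the slope, which would then be read as a relation between populations.

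**Working it through.** **Inputs.** r = 0.85; n = 5, 7 (effective) and 10; α = 5% (all D.7.2 item 3). k is the number of covariates, counting a sex term as one.

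**Reproducing the plan.** Fisher's Z power = Φ(atanh(r)·√(n − 3 − k) − z), with atanh(0.85) = 1.256 and z = 1.645 (one-sided) or 1.960 (two-sided). With k = 0, one-sided:

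- n = 5: Φ(1.256 × √2 − 1.645) = 55.2%
- n = 7: Φ(1.256 × 2 − 1.645) = 80.7%
- n = 10: Φ(1.256 × √7 − 1.645) = 95.3%

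These match the stated 55, 80 and 95%. Two-sided, the same cases give 42.7, 71.0 and 91.4%, which do not match. The plan's figures are therefore one-sided and without covariates.

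**Power with covariates.** D.7.1.3 specifies a regression, so a simulated slope t-test is shown beside Fisher's Z (bivariate normal, unweighted, n − 2 − k degrees of freedom). Two assumptions are not given in the documents: r stays at 0.85 after adjustment, and the effective n of 7 still applies after adjustment. Entries are one-sided (two-sided).

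| Case | Fisher's Z | Slope t-test |
|---|---|---|
| n = 7, k = 0 | 81% (71%) | 88% (79%) |
| n = 7, k = 1 | 70% (59%) | 80% (68%) |
| n = 7, k = 2 | 55% (43%) | 69% (52%) |
| n = 5, k = 0 | 55% (43%) | 69% (52%) |
| n = 5, k = 1 | 35% (24%) | 51% (32%) |
| n = 10 as independent, k = 2 | 88% (80%) | 92% (86%) |

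Sensitivity to r at n = 7, Fisher's Z, for r = 0.80 to 0.90: k = 1 gives 60–82% one-sided (48–72% two-sided), and k = 2 gives 46–67% (34–55%).

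**Effect of leaving sex out of a ten-point analysis.** The inputs are the Table 1 means and SDs by sex and the population BMI rows. Women have higher population BMI than men at all five sites. They also have lower activity counts, AEE/kg and weight-adjusted AEE at all five, although some gaps are very small (weight-adjusted AEE: 15 kcal/d in Maywood, 12 in South Africa; BMI in Nigeria: 0.3). AEE in kcal/d is lower in women at three sites, equal at one and higher at one. Correlations are unweighted. Slopes use D.7.1.3's direction and weighting (mean AEE on mean BMI, weights n/SD²).

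| Metric | r, ten points | r, centred by sex | Slope, no sex term | Slope, sex term |
|---|---|---|---|---|
| Counts/d | −0.22 | +0.27 | −8648 | +6408 |
| AEE/kg | −0.06 | +0.33 | −0.16 | +0.24 |
| Weight-adjusted AEE | +0.10 | +0.46 | −3.0 | +24.4 |
| AEE, kcal/d | +0.39 | +0.69 | +22.5 | +50.8 |

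Omitting sex moves every metric toward the hypothesised negative sign. Three of the four weighted slopes change sign when sex is added; kcal/d does not.

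**False positives.** I simulated no AEE–BMI association within sex, using the Table 1 sex gaps and between-site SDs, an assumed male-female site correlation of 0 to 0.8, and the one-sided 5% Fisher's Z test at effective n = 7. Rejection rates were roughly 4–6% for kcal/d, 6–11% for weight-adjusted AEE, 7–13% for AEE/kg and 12–19% for counts. With no sex gap they were about 2–5%.

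**The case against.** Four arguments on the other side have weight.

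First, a reader might infer that the target can be met only one-sided and without covariates, whatever the number of points. The figures do not support that: ten independent points give 91% two-sided with no covariate and 88% one-sided with two. The restriction applies at effective n = 7. That is still the relevant case, because the plan itself discounts the ten points.

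Second, Fisher's Z is conservative at these sizes, and D.7.2 says weighting will add power. By the slope t-test, one covariate at effective n = 7 still gives about 80% one-sided. This narrows the shortfall. It does not rescue five sites (69% one-sided without covariates) or two covariates at n = 7 (69%), and the gain from weighting is not quantified.

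Third, the covariate sentence in D.7.1.3 could bring in sex, since gender is a listed confounder for the individual-level analysis. That sentence follows the comparison of means and comes before the meta-regression text, which names only intake. If sex is included, the stated 80% still omits its cost.

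Fourth, much is already disclosed. The plan prints the 55%, acknowledges ecological confounding, tests individual-level relationships first as a guard, and says in D.8 that the project does not depend on the group comparisons. This limits the consequence. It leaves the conflict over the unit unresolved.

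**Conclusion.** The concern holds in a bounded form. D.7.2 reaches 80% for H3 only through sex-by-site means at effective n = 7, tested one-sided without covariates. The paragraph beside it describes five units, for which the plan's own figure is 55%, and D.7.1.3 specifies a model with covariates that neither figure reflects. At effective n = 7, one-sided power is 70% (Fisher's Z) to 80% (t-test) with one covariate, and 55% to 69% with two. These figures rest on the two assumptions stated in the working.

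A ten-point analysis without a sex term would mix a male-female contrast into a between-population claim. The effect is least for AEE in kcal/d and largest for activity counts, so the choice of metric matters. The pilot cells hold 16 to 23 people and the text after Table 1 cautions against sub-group interpretation, so these data show direction only. A reader might infer that the pilot already gives spurious support for H3. It does not: the most negative ten-point correlation is −0.22, and for AEE in kcal/d it is positive.

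Nor does this put the sample size in doubt. The 500 per site is derived from the weight-change hypothesis.

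**What to change.** Reconcile the two paragraphs of D.7.2 item 3 on one unit of analysis. In D.7.1.3, state that unit, the AEE metric, the sidedness of the H3 test and a small, fixed number of intake covariates. If sex-by-site means are used, include a sex term (or centre both variables within sex) and model the fact that the two sexes share a site.

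Then restate power in D.7.2 item 3 for that model. Name the test, state the assumptions about the adjusted r and the effective n, and show a range such as r = 0.80 to 0.90. If five sites remain the unit, label 55% as one-sided and unadjusted, and give the figure after one intake covariate beside it.

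The cost is SAP wording, one degree of freedom for sex and a less favourable stated power. No new data are needed and the sample size does not change.

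### The comparison of mean AEE between the most and least obese groups cannot test Hypothesis 3, because it has one population on each side and no between-population error term

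*Combined protocol and SAP*

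**What the plan says.** Hypothesis 3 is one of the four primary hypotheses listed in D.7.1. D.7.1.3 assigns it to a meta-regression over populations: "mean AEE values will be regressed on mean obesity/relative weight values, weighting by the inverse of the squared standard error of the mean AEE values". D.7.2 item 3 gives power for a Fisher's Z test on the group means, stating "We anticipate that the correlation between mean AEE levels and mean body composition will exceed 0.85" and "A Fisher's Z-transformation 5%-significance test will have over 55% power to detect this correlation with 5 values corresponding to the 5 sites". It then gives over 95% power for ten sex-by-site means and 80% for an effective seven.

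The same paragraph ends with a further option: citing the strength of the prior hypothesis, it says the study can also "compare mean AEE in the groups with the highest and lowest rates of obesity to test the ecological association". No test statistic, significance level, sidedness, error term or decision rule is attached to it. For comparing sites, D.7.1.3 says: "The 2 sample t-test will be used to compare means of the primary continuous variables, e.g., BMI, PA, weight, and height". The following paragraph of D.7.2 makes the group average the unit of analysis. It warns that "the causal process could be entirely different from, but simply co-linear with, the AEE relationship" and relies on examining individual-level relationships first.

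**The concern.** Hypothesis 3 concerns variation among populations, so the error against which it is judged must come from variation among populations. A highest-versus-lowest contrast has one population at each end and therefore no replication at that level. A t-test on individuals fills the gap with between-person variation, which shrinks as more people are enrolled, whereas the variation between populations does not. With hundreds of people per group the test is likely to reject if the two communities differ in AEE for any reason, such as occupation, season or setting. When the more obese community happens to have the lower AEE, that rejection would read as support for a primary hypothesis.

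**Working it through.** **The plan's own figures.** Power = Φ(atanh(0.85)·√(n−3) − z), with atanh(0.85) = 1.256. One-sided, z = 1.645:

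- n = 5: Φ(1.777 − 1.645) = 55.2%
- n = 7: Φ(2.512 − 1.645) = 80.7%
- n = 10: Φ(3.323 − 1.645) = 95.3%

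These match the stated powers. Two-sided, they would be 42.7%, 71.0% and 91.4%, so item 3 is implicitly one-sided. Simulating that Fisher's Z test with no association, and treating groups as independent, gives one-sided error of 4.4%, 4.7% and 4.8% for 5, 7 and 10 groups. Keeping the population as the unit therefore holds the nominal level. No error rate is stated for the two-group contrast.

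**Inputs for the contrast.** Site means, SDs and numbers by sex come from Table 1. Planned numbers come from D.7.1.1.1 and D.3.2: 500 per site with accelerometry, so 250 per sex, and 75 per site with DLW. The test is assumed to be the two-sample t-test on individuals.

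**Formulas.**

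- Between-site variance: τ² = variance of the five site means − mean of s²/n.
- s is the pooled within-site SD.
- SE of the difference = s·√(2/N), with N people per group.
- If site means are normal and unrelated to obesity, the observed difference has SD √(2τ² + SE²).
- One-sided rejection rate in the hypothesised direction = 1 − Φ(1.645·SE / √(2τ² + SE²)).

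**Worked case: women, kcal/d, N = 250.** The variance of the five means (884, 1090, 608, 617, 1000) is 48,397 and the mean s²/n is 7,749, so τ = √40,648 = 201.6. With s = 403.8, SE = 403.8·√(2/250) = 36.1. The SD of the difference is √(2·40,648 + 36.1²) = 287.4. The rate is 1 − Φ(1.645·36.1/287.4) = 1 − Φ(0.207) = 41.8%.

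**Lower bound for τ.** Replace the variance of the means by variance·4/11.14, where 11.14 is the 97.5% point of χ² on 4 df, then subtract the mean s²/n.

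| Measure (Table 1) | τ | s | N=250 | N=500 | N=75 | lower τ | N=250 at lower τ |
|---|---|---|---|---|---|---|---|
| AEE kcal/d, men | 139.4 | 303.9 | 41.1% | 43.7% | 34.4% | 58.8 | 30.5% |
| AEE kcal/d, women | 201.6 | 403.8 | 41.8% | 44.2% | 35.5% | 98.1 | 33.9% |
| AEE/kg, men | 1.61 | 4.34 | 39.1% | 42.2% | 31.3% | 0.44 | 19.3% |
| AEE/kg, women | 1.71 | 4.63 | 39.1% | 42.2% | 31.2% | 0.63 | 24.3% |
| AEE adj. for weight, men | 107.2 | 303.3 | 38.6% | 41.8% | 30.5% | 23.7 | 15.0% |
| AEE adj. for weight, women | 139.3 | 368.7 | 39.3% | 42.3% | 31.5% | 52.8 | 25.3% |

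The N = 75 column borrows the accelerometer spread for DLW. The N = 500 and N = 75 columns apply the sex-specific spread to a whole site.

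**Behaviour.** The rate is 5% only when τ = 0, and it approaches 50% as N or τ grows. If τ were only 0.1 to 0.2 of s, it would be 19% to 31% at 250 per group.

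**The case against.** The strongest reply is that the sentence is a minor option in a power section. The meta-regression is the stated analysis, and nothing gives the contrast precedence. D.8 says the project's success does not depend on the group comparisons, and B.7 looks for agreement at both individual and population level. That limits the consequence, but the contrast is still offered as a test of a primary hypothesis. Examining individual-level relationships first addresses ecological confounding; it does not supply the missing error term.

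Second, the t-test is inferred, since item 3 names none, and D.7.1.3 also allows covariate-adjusted models. The inference is reasonable but remains an assumption. Covariate adjustment would not create replication of populations.

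Third, the between-site spread is poorly known: five sites, with 16 to 23 people per sex-by-site cell. Pilot mean age ran from 27.2 to 38.9 years, and the Jamaican and South African men were mainly laborers. B.2 also cites a review finding no systematic activity difference between developed and developing countries. This stands, and is why the rate is given as a range. On raw activity counts in men, the lower bound for τ² falls below zero (3.40×10⁹·4/11.14 = 1.22×10⁹, against a mean s²/n of 1.45×10⁹). For that measure, a spread of zero and a rate of 5% cannot be excluded.

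Three stronger readings are tempting and not supported:

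- A reader might infer that the contrast is held in reserve for an inconclusive regression. The text offers it only as an addition.
- A reader might infer that a difference in either direction would count as support. Only significantly lower AEE in the more obese group would, and the 39–44% is for that direction alone. A two-sided 5% test would reject in one direction or the other 73–81% of the time at 250 per group.
- A reader might set Nigeria against Maywood in Tables 1 and 3 and conclude that the contrast gives opposite significant answers. Those tables differ in instrument, sample and scaling. In Table 3, weight-adjusted DLW AEE is 810 (311) against 765 (299), unstarred, with t about 1.3.

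**Conclusion.** The concern holds in this limited form: as written, the highest-versus-lowest contrast is not a valid test of Hypothesis 3. With one population per side, the t-test on individuals cannot separate an association with obesity from ordinary differences between two communities. The size, about 39–44% for the accelerometer sample and 31–36% for DLW in place of a nominal one-sided 5%, depends on the inferred t-test, normal site means and the pilot spread. At the lower 95% bound of that spread, the six AEE measures give about 15–34% at 250 per group. The exact rate is uncertain; the absence of a between-population error term is not. The weighted meta-regression across all groups is unaffected by this point.

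**What to change.** In D.7.2 item 3, end the sentence about the highest and lowest groups at the word obesity, removing the clause that makes the comparison a test. State that the contrast is descriptive, reported as means with confidence intervals, separately by sex, with no p-value for Hypothesis 3. State there and in D.7.1.3 that the conclusion on Hypothesis 3 rests on the weighted meta-regression across all site (or sex-by-site) means.

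This is a wording change that needs no new data. The cost is the loss of an optional supplementary test.
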